12.0 DATA AND SAFETY MONITORING	26
13.0 QUALITY ASSURANCE AND AUDITS	27
14.0 REFERENCES	28
15.0 APPENDIX	30

ABBREVIATIONS

AE	Adverse Event
ALB	Albumin
ALT	Alanine Aminotransferase
AST	Aspartate Aminotransferase
BUN	Blood Urea Nitrogen
CBC	Complete Blood Count
CMP	Comprehensive Metabolic Panel
CP	Child Pugh
CR	Complete Response
CT	Computed Tomography
CTCAE	Common Terminology Criteria for Adverse Events
CTO	Clinical Trials Office
DLT	Dose Limiting Toxicity
DSMB	Data and Safety Monitoring Board
DSMC	Data and Safety Monitoring Committee
DSMR	Data and Safety Monitoring Report
GTV	Gross Tumor Volume
H&P	History & Physical Exam
HRPP	Human Research Protections Program
IRB	Institutional Review Board
IV (or iv)	Intravenously
MTD	Maximum Tolerated Dose
NTCP	Normal Tissue Complication Probability
OS	Overall Survival
PD	Progressive Disease
PFS	Progression Free Survival
PI	Principal Investigator
PR	Partial Response
PRC	Protocol Review Committee
PTV	Planning Target Volume
QOL	Quality of Life
RT	Radiotherapy
SAE	Serious Adverse Event
SBRT	Stereotactic Body Radiotherapy
SD	Stable Disease
TBILI	Total Bilirubin
UaP	Unanticipated Problem
UMCCC	University of Michigan Comprehensive Cancer Center
WBC	White Blood Cells

STUDY SCHEMA

STUDY SYNOPSIS

Title	A Pilot Study of Individualized Adaptive Radiation Therapy for Intrahepatic Cancer
Methodology	Single arm
Study Duration	2 years
Study Center(s)	Single-center
Objectives	Determine the safety and efficacy of individualized adaptive radiation therapy for intrahepatic cancer
Number of Subjects	80 evaluable patients
Inclusion Criteria	Patients who have hepatocellular carcinoma
Exclusion Criteria	Patients who have a known allergy to intravenous iodinated contrast agents or a contraindication to contrast-enhanced MRI
Study Product(s), Dose, Route, Regimen	Radiation dose and distribution within the liver adjusted based on function and tolerance of first phase of treatment. 3/5 of treatment delivered, followed by 1 month break, followed by the remaining 2/5 of treatment, with dose and spatial distribution adjusted based on biomarker and imaging tumor and normal tissue response.
Duration of Administration	3-5 treatments, depending on ICG, CP score, ALBI score and NTCP model
Statistical Methodology	This pilot study will establish the feasibility of this individualized adaptive radiation therapy. It will also provide preliminary estimates of the safety and efficacy of this treatment that will be used to plan a subsequent randomized controlled trial.

1.0 BACKGROUND AND RATIONALE

1.1 Disease Background

1.1.1 Epidemiology and scope

Worldwide, primary liver cancer is a major health problem with more than 500,000 new cases diagnosed yearly. It is the fifth most common neoplasm, and the third most common cause of cancer-related death.¹ In some areas of Asia, HCC is the most common cause of death due to cancer. The American Cancer Society estimates that 33,190 people will be diagnosed with HCC or intrahepatic cholangiocarcinoma in the US in 2014². The incidence has been increasing in Europe³ and in the US^{2,4} and it is estimated that its incidence in the US will equal that currently reported in Japan within two decades.⁵ Primary liver cancer is one of 4 cancer sites that has increased death rates between 1990 and 2004, and is the only cancer that has shown more than 10% increase (41% and 28% rate increases for males and females, respectively).² This disease is clearly a growing problem.

1.1.2 Current Therapies for unresectable intrahepatic cancer

Complete resection is the most effective therapy for HCC. Unfortunately, curative surgery cannot be offered to most patients. Many patients are inoperable due to comorbidity, and others present with disease extent that requires resections that would not leave sufficient residual functional liver parenchyma. For instance, Abdalla et al. reported the M.D. Anderson experience with hepatic resection.⁶ Of 418 patients who were deemed resectable and were explored, only 190 patients (45%) underwent complete resection. Three major therapies have been used for these unresectable patients.

1.1.2.1 Radiofrequency Ablation (RFA)

In a prospective trial by Lencioni and colleagues⁷, 10% of 206 patients initially evaluated for RFA had contraindications based on tumor location. After these patients were excluded, 20% had an inadequate response to RFA (viable tumor remaining after 1 month). Of the patients who had an inadequate response to RFA, only approximately half of the patients were controlled by a second RFA. Finally, 10% of patients who were thought to be controlled recurred locally within 3 years. In a systematic review of the use of RFA for HCC, local failures over a 3 year period tend to average from 10 - 29%, and failure elsewhere in the liver approximately 50%.⁸ In the case of metastases from colorectal cancer, recurrences after RFA range from 2-39%, with other liver failures from 14-58%.⁸ In all series, local failure increases with tumor size > 3-4 cm. Our experience at the University of Michigan suggests a similar or somewhat higher local failure rate.⁹ In this proposal, we anticipate focusing on patients who have recurred after RFA or have tumors that are not amenable to RFA, such as tumors greater than 3.5 cm in size, as well as those abutting vasculature, lung, or bile duct.

1.1.2.2 Transcatheter Arterial ChemoEmbolization (TACE)

Although some trials and an initial randomized trial showed no difference between chemoembolization and best supportive care^{10,11} more recent studies have begun to suggest that chemoembolization can improve survival of a subset of patients with hepatocellular carcinoma.^{12,13} A systematic review of all modern randomized trials suggests that TACE modestly prolongs survival (from approximately 16 months to 20 months), compared to best supportive care, for patients with tumors < 6 cm who have excellent performance status and do not have portal vein thrombosis^{14,15}. However, TACE is not a curative therapy and tumors typically recur even after multiple TACE administrations,

suggesting that additional therapies are required.

1.1.2.3 Radiation Therapy

In our previous series of prospective clinical trials,^{16,17} we found improved survival with higher radiotherapy dose. Further, dose delivered was the most important predictive factor for survival. Indeed, approximately 20% of patients receiving >75 Gy using 1.5 Gy BID are alive 4 years after treatment; historically that number would be very close to 0%. These data are proof of principle that focused radiation can control intrahepatic cancer, and that we are experienced in these techniques.¹⁸ Since the mid 2000s, stereotactic body radiotherapy (SBRT) has gained in popularity, due to the improvement in convenience, with 5, rather than 30 or more treatments. We have recently published our results, which are in line with other experiences. In the immediately preceding study, we used stereotactic body radiotherapy to successfully and safely treat liver tumors, with 97% 1 year local control and no significant liver toxicity.¹⁹ High efficacy and safety were obtained by individualizing treatment based on not only pre-treatment liver function, but also each patient's tolerance to radiation. In this new protocol, we intend to test our ability to further individualize and adapt treatment based on the geometric distribution of functional liver parenchyma for patients with larger tumors and poor liver function.

[figure not shown]
1.1.3 Avoidance of Radiation Induced Liver Decompensation (Change in CP and ALBI score)

Classically, radiation liver damage was measured with the endpoint of radiation induced liver disease (RILD) based on prior work on whole liver radiation^{20,21}. However, in the modern era with daily imaging and highly conformal radiotherapy, RILD is very rare²². Currently, radiation liver toxicity is more aptly defined by functional liver decompensation in terms of the development of portal hypertension, new onset ascites, and encephalopathy as well as objective lab values. Many groups have published on a change in Child-Pugh score of greater than or equal to 2 and change in the albumin and bilirubin (ALBI score) as more meaningful endpoints²³⁻²⁶. One of the key hypotheses of this trial is that by avoiding functional liver and adapting dose based on liver function, we will minimize these toxic effects. The patients who are at highest risk of decompensation are patients who have poor liver function at baseline. Most patients with HCC present with concurrent cirrhosis which puts them at higher risk of decompensation post radiation. Using spatial functional information as well as direct global measures of liver function e.g. ICG, baseline CP score and ALBI, we hope to deliver a tumoricidal dose without causing toxicity.

1.1.4 Adjusting global RT dose based on liver function as assessed through clearance of Indocyanine Green.

Although we developed the most accurate population-based model for predicting RILD for patients receiving fractionated radiation therapy, we are aware that there are limitations when applying this to individual patients, with variable sensitivity to radiation. Relying solely on the model unnecessarily exposes patients with high sensitivity to radiation to a high risk of toxicity, while at the same time, it also denies patients with average and low sensitivity to higher doses of radiotherapy, which could increase tumor control. In the preceding clinical trial, we individualized therapy based on the sensitivity of individual patient. Initial liver function was characterized by measuring the clearance of indocyanine green, a dye taken up by the plasma almost exclusively by the hepatic parenchymal cells and secreted entirely into the bile without undergoing any significant extrahepatic or enterohepatic circulation. It has been used extensively to predict mortality after liver resection and severe trauma^{27,28}. We delivered 3 treatments of SBRT, waited 4 weeks to detect subclinical decline in liver function, and adjusted radiation dose for 2 remaining treatments, based on the stability or decline in

function¹⁹. Insertion of a treatment break did not compromise tumor control. Indeed, 1 year local control for the first 76 patients was 97%, comparable to any other prospective or retrospective report. Patients with very poor liver function (Child Pugh B and even C) were treated safely on trial, suggesting that modifying radiation dose part-way through treatment successfully avoided what would have been severe toxicity. Our initial analysis of the first 20 patients evaluable on the study showed that we need to begin adapting treatment prior to the first 3/5 of radiation delivery. We plan to accrue an additional 40 patients to examine the feasibility of up front individualization in addition to mid treatment adaptation to minimize toxicity and maintain excellent local control. We have demonstrated that patients with good liver function and small tumors (<3.5 cm) have excellent local control and very low rates of toxicity. The current protocol looks at adapting therapy for patients with good liver function (CPA to B7) but larger tumors where more liver parenchyma would receive radiation thereby increasing the risk of toxicity and those with poor liver function (CPB8 and above) who at baseline are at increased risk of liver decompensation post treatment. Our interim analysis has revealed that a combination of albumin and bilirubin, called ALBI, which is an accurate predictor of survival for patients with HCC with liver dysfunction³⁶, is as or more useful than ICG in estimating liver function and predicting future toxicity. Thus, either ICG or ALBI can be used in this trial.

1.1.4.1 Adjusting spatial RT distribution based on regional liver function as assessed by perfusion MRI. This protocol builds on over 25 years of experience with high dose liver RT, and in particular adaptive RT aimed at adjusting the global radiation dose based on a patient's measured sensitivity to treatment. The next leap forward is to use functional imaging to spare highly functional portions of the liver. We have previously demonstrated that dynamic contrast-enhanced (DCE or perfusion) MRI correlates with global liver function as measured by ICG, and that regionally, function declines as a function of delivered radiation dose.²⁹ This and, potentially, other advanced MRI techniques, provides the opportunity to sculpt dose away from high-functioning parts of the liver to improve the safety of treatment.

1.2 Study Agent(s) Background and Associated Known Toxicities

We have over 25 years of experience with liver radiotherapy. As discussed above, change in Child Pugh status and ALBI are the primary toxicity endpoints. Additionally, depending on the tumor location and proximity to normal structures including stomach, small bowel, colon, and right kidney, there is a small risk of GI bleed or renal damage. These are quite rare in our experience, minimize with careful treatment planning and delivery. Indocyanine green is FDA approved and has been in use for 50 years to estimate liver function. In patients without an iodine allergy, it is quite safe. Patients with iodine allergies will be excluded from participation in this study.

1.3 Rationale

This is a pilot single arm study with a goal of obtaining preliminary estimates of safety and efficacy. This protocol builds on over 25 years of experience with high dose liver RT, and in particular adaptive RT aimed at adjusting the global radiation dose based on a patient's measured sensitivity to treatment. Using functional imaging to spare highly functional portions of the liver is a novel concept, and as far as we know, we are the only ones currently in a position to put this into practice. We feel this will further improve the safety and efficacy of RT for all patients by customizing treatments to each. If this approach is promising, we will proceed to a phase II randomized study of standard versus spatially and dosimetrically adapted RT.

1.4 Quality of life

The quality of life of patients with liver tumors is not well-studied. For these patients, many of whom already suffer from chronic medical problems including cirrhosis, it is particularly important to understand how tumor-directed treatments impact quality of life. The Functional Assessment of Cancer Therapy-Hepatobiliary (FACT-Hep) version 4

questionnaire will be used in this study to measure QOL. This is a 45-item validated instrument used in other clinical trials of treatment for liver cancer, including the RTOG 1112 international randomized trial of sorafenib +/- SBRT.

1.5 Correlative Studies

1.5.1 Assessment of plasma and serum biomarkers: Classic RILD is caused by veno-occlusive disease, which is likely related to endothelial cell apoptosis as an initiating lesion. Radiation also induces various proinflammatory cytokines, including tumor necrosis factor-alpha (TNF-alpha) and transforming growth factor-beta 1,³⁰ and hepatic microvascular pathogenesis that lead to apoptosis in the liver.³¹ Elevation of TGF-beta has been associated with RILD in women undergoing bone marrow transplantation for breast cancer³². In addition, an increased TNF-alpha production has been associated with the progression of hepatic veno-occlusive diseases in stem cell transplant patients³³, suggesting the potential role of cytokines in radiation-induced liver apoptosis. Our preclinical studies demonstrate the TNF alpha may play a key role in radiation injury of the liver.³⁴ We have experience measuring cytokines in patient plasma. We propose to measure these cytokines and other potential circulating biomarkers in plasma and serum, and retrospectively assess their potential contribution to individualize our assessment of liver injury that could be used to adjust liver dose.

2.0 STUDY OBJECTIVES

2.1 Primary Objectives

- 1) Establish the feasibility of the proposed adaptive treatment strategy
- 2) Obtain preliminary estimates of the safety and efficacy of individualized adaptive RT.

2.2 Secondary Objectives

- 1) To collect data on biomarkers of treatment efficacy, toxicity, and liver function to plan further enhancements to individualized RT.
- 2) To determine the change in quality of life during and after RT.

2.3 Endpoints

2.3.1 Primary endpoints:

- 2.3.1.1 Feasibility: Successful completion of treatment including use of perfusion MR in plan optimization.
- 2.3.1.2 Safety: Rate of liver decompensation (change in Child-Pugh score >2 and ALBI score > 0.5) and grade 3 GI bleeding. The former are lab values that are already collected as standard of care. The latter will be assessed via the NCI CTCAE version 4.0.
- 2.3.1.3 Efficacy: Lesion-specific local control

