3.1 Inclusion Criteria

- 3.1.1 Patients with hepatocellular carcinoma are eligible for this trial. Hepatocellular carcinoma is defined as having at least one of the following:

- a. Biopsy proven hepatocellular carcinoma (HCC); or
- b. A discrete hepatic tumor(s) as defined by the Barcelona³⁵ criteria – for cirrhotic patients, >1cm with arterial hypervascularity and venous or delayed phase washout on CT or MRI [RECIST or mRECIST measurements will be captured for the study database and response assessment, however documentation of RECIST or mRECIST is not required at the time of enrollment.]

- 3.1.2 Patients must not have extrahepatic cancer.
- 3.1.3 Patients must not be eligible for curative liver resection or has refused resection.
- 3.1.4 Patients must have recovered from the acute effects of prior liver-directed therapy (e.g. RT, RFA, or TACE), and a minimum of 4 weeks must have passed since the last procedure and protocol therapy.

- 3.1.5 Patients must have a Zubrod performance status of ≤2.
- 3.1.6 Patients must have a life expectancy of at least 12 weeks.
- 3.1.7 Patients must be 18 years of age or older.
- 3.1.8 Patients must have adequate organ function as defined below.
 - Bone marrow: Platelets ≥30,000/mm³
 - Renal: BUN ≤40 mg/dl; creatinine ≤2.0 mg/dl
 - CPB score 8 and above for any size tumor
 - CPA-B7 score with tumors >3.5 cm
- 3.1.9 Patients must understand and be willing to sign an informed consent form approved for this purpose by the Institutional Review Board (IRB) of the University of Michigan Medical Center indicating that they are aware of the investigational aspects of the treatment and the potential risks.

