5.1.2 Initial radiotherapy plan

5.1.2.1 CT with or without MRI simulation will be performed in treatment planning position, with appropriate immobilization, as is standard of care.

5.1.2.2 Radiation target volumes. The gross tumor volume (GTV) will be defined on CT or MRI. Appropriate patient-specific margins for motion will be added for patients unable to tolerate breath hold for treatment. No margin will be added for microscopic extent, as per routine clinical practice. A PTV margin will be added as per standard practice, typically 5mm radially and 8mm superiorly and inferiorly.

5.1.2.3 PTV Target Doses. Doses will be prescribed to a peripheral covering isodose covering the PTV, except in cases where this would exceed recommended doses to organs at risk (OARs). In these cases, heterogeneous dose distributions sparing these OARs are expected. The dose per fraction will be determined by the risk of liver damage, which will be fixed at $\leq 10\%$ for the initial 3/5 of treatment. The full treatment plan will be devised at this time in order to account for total normal tissue dose if patients are able to proceed with the entire treatment. The remaining 2/5 of treatment will be determined as per section 11 and potentially reduced based on liver function. Maximum prescribed tumor dose will be 55 Gy in 5 fractions, which we have shown that this dose is adequate for 95% local control at 2 years even for large tumors.

5.1.2.4 OAR Limits. Standard OAR limits in routine clinical practice will be applied and will take priority over target coverage.

5.1.3 Radiation Schedule. The first 3/5 of the treatment plan will be delivered in the initial phase. The dose of radiation will be based on baseline ICG or ALBI, CP score, and functional liver imaging for an NTCP < 10% for a predicted CP score change of greater than or equal to 2. After an approximately 4 week break and re-assessment of liver function with ICG testing or ALBI, the final 2/5 of treatment may be delivered, as per section 11. Patients who have, or would be predicted to have, unacceptable Toxicity (as defined in section 8.6) at the reassessment point will receive no additional therapy at that time.

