5.2 Toxities and Dosing Delays/Dose Modifications

Patients who receive radiation treatment on this protocol will be evaluable for toxicity. Toxicity will be assessed according to the NCI Common Terminology Criteria for Adverse Events (CTCAE), version 4.0. If these toxicities occur **during treatment**, then RT will be held until resolution: Grade ≥ 3 ascites, change in ALBI score by 0.5, Child Pugh score greater than or equal to 2.

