11.0 STATISTICAL CONSIDERATIONS

11.1 Study Design

This is a pilot study of individualized adaptive RT, which consists of 3/5 of a planned total course of treatment, a one month break, assessment of global and spatial liver function change using IC-Green or ALBI, and perfusion MRI, and the remainder of treatment adjusted for global and spatial changes in liver function. The primary endpoints are to establish the feasibility of this approach and to obtain preliminary estimates of safety and efficacy both overall and as they relate to treatment and patient characteristics. At the completion of this trial we will have the necessary data to define a SBRT treatment approach that is individualized and adaptive and ready to be compared to standard SBRT in a randomized trial.

Patients will have an initial plan with total dose chosen such that the estimated probability of toxicity (increase in CP of 2 points or more within 6 months of RT) from the first three of five planned treatments is at most 10%. In order to protect the safety of individual patients, after delivering 60% of the planned total treatment, there will be a 1 month break at the end of which, ALBI or ICG will be measured again and a new treatment plan will be developed.

This last course of treatment may be adapted (relative to the first course) globally in one of 2 ways. First, if there is no remaining enhancement on the MRI scan, no further radiation will be given because the tumor is likely to be cured. The second possible adaptation is intended

to prevent clinically significant decline in liver function in patients whose livers appear to be sensitive to RT. Child-Pugh (CP) score is a standard measure of liver function, and an increase of 2 points or more on this scale is considered clinically significant. Early changes in ICG retention and ALBI reveal subclinical changes in liver function that predict later liver toxicity, assessed by a change of 2 in CP score 6 months after treatment.

Maximizing tumor control and minimizing liver toxicity are competing objectives when selecting RT dose for these patients. To make this tradeoff explicit and quantitative, the dose during the second course of treatment will be selected as the minimum of

- 1) The dose that maximizes $\text{Prob}(\text{Local Control at 1 year}) - 4 * \text{P}(\text{Toxicity})$
- 2) The dose associated with a 25% estimated risk of toxicity.

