11.2 Sample Size and Accrual

This is a pilot trial to gather the data necessary to plan a randomized phase II study with a control group receiving standard therapy. The planned accrual is 80 evaluable patients over two years. An evaluable patient is a patient that has received their complete prescribed treatment (including those whose ICG measurements or ALBI precluded the second phase of treatment and those for whom other toxicity prevented them from receiving a full course of treatment). The high level goal of this trial is to define an individualized and adaptive approach to use of RT in this patient population. Key components of individualizing and adapting treatment are models that relate expected toxicity and tumor control outcomes to RT dose and other patient level characteristics. Part of the reason for the sample size of 80 is to refine these models prior to initiating a randomized trial. For toxicity, our preliminary data suggests that mean liver dose (or some other measure of dose to normal liver), baseline liver function (e.g. CP score) and mid-treatment change in ICGR15 are the most important factors. If our overall event rate for toxicity is about 20%, we expect to have approximately 16 toxicity events which, in combination with some data from similarly treated previous patients, should be sufficient to estimate parameters in a toxicity model with 3 predictors. For tumor control, tumor dose is expected to be the most significant predictor. There will likely be a lower rate of local progression events so that this model may need to have fewer predictors. In addition to further defining statistical models this trial will permit us to estimate rates of toxicity and tumor control that will be key when designing a randomized trial with power to reject a specific null hypothesis.

This treatment will be considered sufficiently promising to initiate a phase II trial if it causes toxicity (increase in CP score of 2 points or more within 6 months of treatment) in no more

than 25% of patients and results in a local control rate (at 1 year) of at least 80%.

We expect to be able to accrue 20 patients per year and thus to complete accrual in approximately 4 years.

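### Section 2.3.1.2 sets the primary safety event at a Child-Pugh change above 2 plus ALBI, while section 11 uses 2 or more within 6 months and makes ALBI secondary

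*Combined protocol and SAP*

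**What the plan says.** The Endpoints section (2.3.1.2) gives primary safety as the rate of liver decompensation, "change in Child-Pugh score >2 and ALBI score > 0.5", together with grade 3 GI bleeding. It sets no time window. Section 1.2 also puts ALBI on the primary side: "change in Child Pugh status and ALBI are the primary toxicity endpoints".

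The other Child-Pugh toxicity definitions use a lower threshold:

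- Section 1.1.3 cites a change of at least 2 as the more meaningful modern endpoint.
- Section 5.1.3 limits the dose of the first phase by the modelled risk of a "predicted CP score change of greater than or equal to 2".
- Section 11.1 defines toxicity as a rise of at least 2 points within 6 months, and says that "an increase of 2 points or more on this scale is considered clinically significant".
- Section 11.2 attaches its 25% toxicity limit to an "increase in CP score of 2 points or more within 6 months of treatment".
- Section 11.3 names as the primary toxicity endpoint a Child-Pugh change of at least 2 within 6 months of SBRT. It lists ALBI changes and the grade 3 toxicities of section 8 as secondary.

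The rule in 5.2 for holding RT during treatment lists grade 3 or worse ascites and then "change in ALBI score by 0.5, Child Pugh score greater than or equal to 2".

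**The concern.** Child-Pugh is scored in whole points, so >2 means 3 or more. The patient who rises by exactly 2 points falls between the two definitions: an event in the 11.3 analysis and under the 11.2 criterion, but not under 2.3.1.2. Obtaining preliminary estimates of safety is part of a primary objective (2.1), and those estimates are meant to inform a randomized trial. The protocol does not say which section governs, so the same data could yield two different primary toxicity rates. On the Child-Pugh threshold, the 2.3.1.2 rate is the more favourable one, because it leaves out rises that the protocol itself treats as clinically important.

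Three further mismatches remain even if the >2 is a slip for 2 or more:

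- ALBI is primary in 1.2 and 2.3.1.2 but secondary in 11.3. The word joining the two measures in 2.3.1.2 also leaves open whether one patient must meet both.
- 2.3.1.2 has no time window, whereas section 11 uses 6 months.
- Grade 3 GI bleeding is primary in 2.3.1.2, whereas 11.3 places grade 3 toxicities among the secondary endpoints.

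**Working it through.** **Definitions side by side**

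| Section | Child-Pugh threshold | Window | ALBI |
|---|---|---|---|
| 2.3.1.2 | >2 | none | part of the primary endpoint |
| 1.2 | not stated | none | primary |
| 5.1.3 (dose limit) | 2 or more | none | not part of the event |
| 11.1 | 2 or more | 6 months | not part of the event |
| 11.2 | 2 or more | 6 months | not part of the event |
| 11.3 | 2 or more | 6 months | secondary |

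**Inputs.** N = 80 evaluable patients and an overall toxicity rate of about 20%, both from 11.2. The share *s* of events that are rises of exactly 2 points is not in the documents; I take 25%, 50% and 75% as an assumed range.

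**The plan's own figure.** Expected events = 80 × 0.20 = 16. This matches the approximately 16 in 11.2, which rests on the definition of 2 or more.

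**The same patients under >2.** Events counted = 16 × (1 − *s*); rate = events counted / 80.

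- *s* = 25%: 16 × 0.75 = 12 events, 12/80 = 15%
- *s* = 50%: 16 × 0.50 = 8 events, 8/80 = 10%
- *s* = 75%: 16 × 0.25 = 4 events, 4/80 = 5%

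These counts compare the Child-Pugh threshold alone over the same 6 months. If a patient must also meet the ALBI condition, the counts can only be lower. If ALBI is a separately listed measure, they stand as shown. Late events admitted by the missing window, or GI bleeds added to a single combined rate, would push the 2.3.1.2 figure the other way; the documents give no basis for sizing either.

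**The 5.2 hold rule.** Read word for word, the Child-Pugh item is an absolute score of 2 or more. Patients at B7 already exceed that at baseline, as do those admitted under "CPB score 8 and above for any size tumor" (3.1.8). The rule can hardly mean this, so the text is ambiguous and no figure attaches to it.

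**The case against.** The strongest reply is that section 11 settles the matter. It is consistent on the Child-Pugh threshold, 11.3 names the primary toxicity endpoint outright, and 2.3.1.2 is the lone outlier. This stands to a large extent: if 11.2 and 11.3 are followed, the sample size, the analysis and the phase II criterion are unchanged. It does not make 2.3.1.2 harmless, because that is the section headed Endpoints and a report could be written from it.

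A reader might go further and infer that the trial could pass its 25% toxicity limit by counting only rises above 2. The documents do not support that. The 11.2 criterion carries its own definition in the same sentence, and the plan nowhere pairs the limit with >2. Any false-pass probability would describe a misapplication of the plan and would rest on an assumed true rate and an assumed share of exact 2-point rises.

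The >2 may also be a typing slip, or a mark lost when the PDF was read. This cannot be excluded, although symbols for at least and at most survive elsewhere, for example in 3.1.8 and 5.2. The ALBI and time-window conflicts do not depend on that symbol.

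It is fair to add that this is a pilot with no hypothesis test on toxicity, so the primary or secondary label for ALBI alters no test. It still alters what is reported as the primary safety rate.

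On 5.2, a reader might infer that the rule would stop RT in every patient. The opening words of the item can carry over from ALBI to Child-Pugh, and the rule concerns toxicities arising during treatment, so that inference fails.

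**Conclusion.** The point holds as a wrong threshold and an inconsistent endpoint definition in 2.3.1.2. Reporting Child-Pugh toxicity by that section would understate it against 11.3: 12, 8 or 4 events in place of 16 of 80, or 15%, 10% or 5% in place of 20%, for the three assumed shares. That 2.3.1.2 conflicts with 5.1.3 and section 11 is certain on the current text; the size is illustrative, since the true share is unknown.

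The reach is limited. The 11.2 criterion, the expected event count and the 11.3 analysis stand as written. The toxicity stopping rule in 8.7 uses radiation induced liver disease and is not touched by this point. The 5.2 item is a minor wording correction.

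**What to change.** 1. In 2.3.1.2, define liver decompensation as an increase in Child-Pugh score of ≥2 within 6 months of RT, to match section 11.
2. List ALBI change >0.5 as a separate secondary endpoint, as 11.3 does for ALBI changes, and align the sentence in 1.2.
3. Keep grade 3 GI bleeding as a separately reported safety endpoint, named with the same status in 2.3.1.2 and 11.3. The documents do not require it to be demoted; the sponsor can choose either status, provided that the two sections agree.
4. In 5.2, insert *change in* before the Child-Pugh item.

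The cost is a few text edits: the endpoint definition, one sentence in 1.2, the status of GI bleeding in 11.3 if needed, and two words in 5.2. The design, the 80 patients, the expected 16 events and the Child-Pugh analysis in 11.3 do not change.
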